PILOT PHASE II MULTICENTER STUDY OF THE PI3K INHIBITOR COPANLISIB IN COMBINATION WITH A KETOGENIC DIET IN THE TREATMENT OF PATIENTS WITH RELAPSED OR REFRACTORY FOLLICULAR LYMPHOMA OR ENDOMETRIAL CANCER

NCT04750941

Protocol date: 9/23/2024

PROTOCOL SYNOPSIS

Study Design: This is a multi-institution, open label, pilot phase II study of the PI3K inhibitor copanlisib in combination with a ketogenic diet in the treatment of patients with one of the following malignancies: (a) relapsed or refractory (R/R) follicular lymphoma (FL), (b) R/R endometrial cancer (EC) with a documented activating mutation in PIK3CA or loss of PTEN. The FL arm will enroll 23 subjects and the EC arm will enroll 19 subjects. The study will be stopped if the safety trigger is activated at the pre-specified times of interim safety analysis upon enrollment of 12 and 24 patients.

The two arms will enroll patients in parallel and independently. Safety analysis will be done by pooling patients from the two arms together. Efficacy analysis will be conducted independently within each arm.

Objectives: Primary Objectives

- Determine the objective response rate (ORR) (complete response [CR] + partial response [PR]) in FL.
- Determine the ORR in EC.

Secondary Objectives:

- Determine the CR and PR rates in FL upon completion of the study protocol.
- Determine the CR and PR rates in EC upon completion of the study protocol.
- Determine the ORR in FL and EC at the Simon stage I analysis
- Determine patient compliance with the ketogenic diet.

Exploratory Objectives:

- Determine the PD markers including *blood* levels of insulin, c-Peptide, BHB (beta-hydroxybutyrate), triglyceride, and glucose, and urine ketones.
- Determine the PD markers including levels of pINSR, INSR, pAKT, AKT, pS6, S6, Ki-67, TUNEL, caspase, and actin in paired pre- and post-treatment *tumor* tissues in patients who consented for the optional post-treatment biopsy of the tumors (blood and bone marrow are acceptable if they are known to be involved by lymphoma).
- Explore the correlation of disease response and the PD markers described above.
- Explore the correlation of disease response and gene alternations in tumor tissues.
- Explore the correlation of insulin response and gene alternations in normal buccal fibroblasts.
- Determine the change in body weight and body mass index (BMI) over time.
- Determine the change in computed tomography-based body composition metrics including

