The Phase II study will enroll 42 patients in two study groups. The lymphoma study group will enroll 23 patients with FL, and the solid tumor group will enroll 19 patients with EC.

In cycle 1, patients will first start ketogenic diet for 7 days (Day -6 to Day 0). Only patients who demonstrate compliance and tolerance with the ketogenic diet for all 7 days during the run-in

phase, as confirmed by pertinent blood and urine tests, will be allowed to continue the study and treatment using copanlisib and the ketogenic diet starting on day 1. In cycle 2 and beyond, patients will start the ketogenic diet and copanlisib on day 1.

Treatment Plan:

- Copanlisib: Copanlisib will be infused intravenously on days d1, 8, 15 of each cycle, over 1 hour, of 28-day cycles.
- Ketogenic diet:
 - Prior to the first treatment patients will start the ketogenic diet for 6 days (Day -5 to Day 0). Patients who demonstrate compliance and tolerance with the ketogenic diet, as confirmed by pertinent blood and urine tests and recorded dietary intake, will be allowed to continue the study and start copanlisib on Day 1. The ketogenic diet will continue daily throughout the treatment days.
 - In cycle 2 and beyond, patients will start the ketogenic diet and copanlisib on day 1. The ketogenic diet will then continue daily throughout the treatment days.
 - All patients will be eligible to receive the ketogenic diet as long as the patients remain on the trial. If patients want to remain on the trial to receive Copanlisib but wish to discontinue the ketogenic diet, they should do so at the following time: (a) when they have achieved a complete response, or (b) when they have completed 4 cycles of treatment. In the rare case when a patient wants to discontinue the ketogenic diet after having completed only 2 or 3 cycles of therapy but having not achieved a CR, the patient will be allowed to remain in the study and receive copanlisib without having to take the ketogenic diet. However, if a patient wishes to stop the ketogenic diet before

cycle 2 is completed, when the response will be first evaluated, the patient will not be allowed to continue this trial but will be replaced.

REGIMEN DESCRIPTION					
Agent	Premedications/Precautions	Dose	Route	Cycle Length	
Copanlisib	IV Hydration (Normal Saline 500 cc IV in 30 minutes after copanlisib infusion)	60 mg	IV over 60 minutes	28 days	
Ketogenic diet		Three times daily	Oral, three times daily		

Dose Modification:

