(RECIST) guideline. CT or PET/CT scan will be performed after every two 28-day cycles of. After cycle 4, if the patient has achieved CR, scans will be done every 3 cycles.

Data analysis:

All patients receiving at least one dose of copanlisib will be evaluable for toxicity and all patients completing at least one 28-day cycle of therapy (copanlisib plus ketogenic diet) will be evaluable for response and time-to-endpoint analyses.

Response will be estimated with exact 95% confidence intervals (CIs). We will estimate overall survival, progression-free survival, and duration of response using the Kaplan-Meier method. Group comparisons, between groups associated with different biomarkers described below, will be made using a two-sided log-rank test, and the estimated hazard ratios and 95% CIs will be calculated using Cox regression. Overall survival will be assessed post hoc in the trial patients. In the exploratory correlative biomarker analyses, any patients with assessable biological samples (blood, tumor etc) will be included. An association between disease outcome (complete response, partial response, stable disease, progression of disease, duration of response, and progression-free survival) and changes from baseline in biomarker concentrations as a function of treatment over time will be assessed. Because of sample size considerations, we will base group comparisons for these analyses on two-sample t test. We will do correlative studies including all enrolled patients that have adequate biological samples available for analysis. We plan to assess changes over time and estimate odds ratios using mixed-effects logistic regression models or a linear model if the sample sizes for comparison are too small. We will summarize continuous variables as means and SDs, and categorical variables as counts with percentages. We will not do multiple testing adjustments. All the analyses will be done with SAS version 9.4.

Study Rationale

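### Diet exposure after cycle 2 can depend on response, but the exploratory marker-response analysis has no on-diet window or diet-status term, so the association can be weakened and, for CR versus non-response, possibly reversed

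*Combined protocol and SAP*

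**What the plan says.** **Diet stopping (Treatment Plan, Ketogenic diet).** Stopping is the patient's choice: "If patients want to remain on the trial to receive Copanlisib but wish to discontinue the ketogenic diet", the times given are "a) when they have achieved a complete response, or (b) when they have completed 4 cycles of treatment". A patient without CR may also stop earlier and stay on copanlisib, but the plan treats this as unusual: "In the rare case when a patient wants to discontinue the ketogenic diet after having completed only 2 or 3 cycles of therapy". A patient who stops before "cycle 2 is completed, when the response will be first evaluated, the patient will not be allowed to continue this trial" and is replaced.

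**Response timing (Efficacy Outcome).** "CT or PET/CT scan will be performed after every two 28-day cycles of" treatment, so the first scheduled chance to document CR is at the end of cycle 2.

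**Markers (Exploratory Objectives).** The blood and urine markers are "levels of insulin, c-Peptide, BHB (beta-hydroxybutyrate), triglyceride, and glucose, and urine ketones". A later objective reads "Explore the correlation of disease response and the PD markers described above". Body weight, BMI, and CT- and PET-based body composition follow as separate objectives about change, with no link to response.

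**Analysis (Data analysis).** Disease outcome (CR, PR, SD, progression, duration of response, PFS) is to be associated with marker change: "changes from baseline in biomarker concentrations as a function of treatment over time will be assessed". All enrolled patients with adequate samples are included. The methods named are two-sample t tests and mixed-effects logistic or linear models. No on-diet window, landmark, diet-status covariate or censoring at diet stop is given.

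The text supplied contains no schedule for PD sampling.

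**The concern.** The diet is expected to move these markers directly. The plan uses blood and urine tests to confirm diet compliance in the run-in, and the Study Rationale reports that the diet mitigates copanlisib-induced insulin in mice. A sample taken after a patient leaves the diet therefore reflects the stop as well as the patient's biology.

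If leaving the diet depends on response, part of the marker-response association runs from response to marker. The direction matters. The trial's premise is that better insulin suppression goes with better response. Off-diet samples from responders push their insulin up and their ketones down, against that premise. A real association could be hidden, and in some contrasts could take the wrong sign, in the analysis that speaks to the trial's proposed mechanism.

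**Working it through.** The plan gives no figure on this point, so there is none to reproduce. The check has four steps.

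**1. Who can be off the diet, and when**

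- Cycles 1-2: every retained patient is on the diet, because an earlier stop means leaving the trial.
- Cycles 3-4: CR is the planned route off the diet. Stopping without CR is possible but described as rare.
- After cycle 4: any patient may stop. Treatment runs to progression, so patients still contributing samples are mostly those still benefiting.

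Diet status is thus uniform up to the first response scan and can depend on response afterwards.

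**2. Illustration with no true link**

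Assumptions: BHB 0.2 mmol/L off diet, one sample per cycle, cycles 1-4 averaged, diet stopped after cycle 2.

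Mean = (2 × on + 2 × 0.2)/4

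- On-diet 1.0: (2.0 + 0.4)/4 = 0.60; 0.60/1.0 = 0.60, 40% lower.
- On-diet 1.5: (3.0 + 0.4)/4 = 0.85; 0.85/1.5 = 0.57, 43% lower.
- On-diet 2.5: (5.0 + 0.4)/4 = 1.35; 1.35/2.5 = 0.54, 46% lower.

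If half of CR patients stop (on-diet 1.5), the CR mean is (0.85 + 1.50)/2 = 1.175, 22% lower. All of this comes from stopping the diet.

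**3. With a true association: attenuation or reversal**

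Score the marker so that higher means a stronger diet effect. Let d be the true on-diet difference (responder minus non-responder), D the loss when off diet, and f the off-diet share of the responding group's visits. Non-responders are taken as on diet throughout.

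Expected contrast = d - D × f; it reverses when D/d exceeds 1/f.

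Assume responders have 8 cycles, every CR patient stops after cycle 2, and nobody else stops. A CR patient then has f = 6/8 = 0.75. Across all responders, f = 0.75 × CR/ORR. The plan gives FL CR rates of 9% (assumed in the sample-size text), 14% (reference) and 30% (target), a reference ORR of up to 59%, and a target ORR of 67%.

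| Contrast with non-responders | f | Reverses when D/d exceeds |
|---|---|---|
| CR patients | 0.75 | 1.33 |
| All responders, CR 9%, ORR 59% | 0.75 × 0.09/0.59 = 0.11 | 8.7 |
| All responders, CR 14%, ORR 59% | 0.75 × 0.14/0.59 = 0.18 | 5.6 |
| All responders, CR 30%, ORR 67% | 0.75 × 0.30/0.67 = 0.34 | 3.0 |

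With d = 0.5 SD and D = 0.5, 1 or 2 SD:

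- CR patients: 0.12, -0.25 or -1.0 SD.
- All responders at CR 14%, ORR 59%: 0.41, 0.32 or 0.14 SD, attenuated but not reversed.

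Expected CRs among 23 FL patients are 23 × 0.09 = 2.1, 23 × 0.14 = 3.2 or 23 × 0.30 = 6.9.

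**4. Simulation of the all-responder contrast**

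There were 23 patients and 5,000 runs per scenario, with d = 0.5 SD, D = 2 SD, 8 cycles for responders and 4 for non-responders (all assumed except the 23).

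| Scenario, all visits used | Mean contrast | Wrong sign |
|---|---|---|
| CR 14%, ORR 59%, nobody stops | 0.49 | 14% |
| CR 14%, ORR 59%, all CRs stop after cycle 2 | 0.13 | 39% |
| Same, and half of the others stop after cycle 4 | -0.24 | 69% |
| CR 30%, ORR 67%, all CRs stop after cycle 2 | -0.17 | 63% |

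Using cycles 1-2 only makes f = 0. The mean returns to about 0.5 in every scenario, with the wrong sign by chance in 14-15% of trials.

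**The case against.** The strongest reply has four parts.

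- **Stopping is elective and not reserved for CR.** A reader might infer that reaching CR itself raises insulin and lowers ketones. The plan does not support that: CR permits an early stop, patients may stay on the diet for as long as they are on trial, and others may also stop. No stopping frequency is given. This stands. The bias needs stopping to differ by response, which the rule makes possible but not certain.
- **The sampling window is unknown.** The analysis text says over time, not over all time. If blood markers are drawn only in the first two cycles, the problem largely disappears. This also stands, and the point is conditional on later sampling.
- **Treatment may include the diet.** The same section describes therapy as copanlisib plus ketogenic diet, and diet compliance is a secondary objective, so diet exposure might be meant to enter the models. That is a possible reading, but the text names no such term and no rule for off-diet samples.
- **The consequence is limited.** These are exploratory analyses in a 42-patient pilot. With only 2-3 CRs expected in FL at 9-14%, a time-varying diet term would be poorly estimated. This stands too, and is a reason to rely on the early window rather than on modelling.

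**Conclusion.** The concern holds in a limited form. As written, the plan lets diet exposure after cycle 2 depend on response and analyses marker change over time without a rule for off-diet samples. If such samples are taken, the exploratory marker-response association can be biased towards or past zero.

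A reader might infer that the correlation as a whole will reverse. The figures do not support that as a general statement. At the reference rates, with only CR patients stopping, the all-responder contrast is attenuated and reverses only if the off-diet shift exceeds about 5.6 times the true difference. Reversal is plausible for CR versus non-response if most CR patients stop and the shift is large. For all responders it needs many CRs, stopping by other responders after cycle 4, or a very large shift. The BHB values, shift sizes, stopping fractions and cycle counts are all assumptions.

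A reader might also extend the point to weight, BMI and body composition. These are outside the response-correlation objective; only their descriptive trends would mix on-diet and off-diet time. Paired tumour-biopsy markers are affected only if the post-treatment biopsy follows diet stop, and its timing is not stated. The primary ORR tests use no marker data and are unaffected.

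**What to change.** In Data analysis:

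1. Base the main association between blood PD markers and response on samples up to the earlier of diet stop and the end-of-cycle-2 scan. Every patient still on trial must be on the diet during this period.
2. Carry the diet-stop date as an analysis variable.
3. For later samples, and for trends in weight, BMI and CT/PET body composition, show on-diet and off-diet data separately, or enter diet status at the time of measurement as a time-varying factor where numbers allow.

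The cost is a change of analysis wording, one derived variable, and fewer late samples in the main correlative analysis. The early window removes the response-dependent exposure but not the imprecision of a small sample. The diet-stopping rule itself is not changed.

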Dose Modification of copanlisib is described in Section 6.6.

Duration of Treatment:

Patients will be treated until one of the following events: disease progression, unacceptable adverse event(s), withdrawal of consent, general or specific changes in the patient's condition that render the patient unacceptable for further treatment in the judgment of the investigator.

Sample Size and Statistical Consideration:

The study will enroll 42 patients. The two arms will enroll patients in parallel and independently. Safety analysis will be done by pooling patients from the two arms together. Efficacy analysis will be conducted independently within each of the two arms (lymphoma, solid tumor).

Patients who do not complete the planned cycle 2 cycles of treatment, which is required for the first evaluation of response, will be replaced.

(a) The lymphoma arm will enroll 23 patients with FL.

- Simon's two-stage design (Simon, 1989) will be used. The null hypothesis that the true ORR rate is 41% will be tested against a one-sided alternative. In the first stage, 13 patients will be accrued. If there are 5 or fewer ORRs (**To be assessed after completing 4 cycles of the treatment**) in these 13 patients, the study will be stopped for futility. Otherwise, 10 additional patients will be accrued for a total of 23. The null hypothesis will be rejected if 14 or more ORRs are observed in 23 patients. This design yields a type I error rate of 5% and power of 80% when the true ORR rate is 67%. Assuming that the CR rate is 0.09 (2 out 23), with 23 subjects we will have 80% power to claim that the true CR is at least 30%.
- The reference range of ORR in FL is 40% (n = 16. Dreyling et al, Ann Oncol. 2017) to

59% (n = 104. Dreyling et al, J Clin Oncol. 2017).

• The reference CR rate is 14% (n = 104. Dreyling et al, J Clin Oncol. 2017).

(b) The solid tumor arm will enroll 19 patients with EC.

Simon's two-stage design (Simon, 1989) will be used. The null hypothesis that the true ORR rate is 0.10 will be tested against a one-sided alternative. In the first stage, 11 patients will be accrued. If there are 1 or fewer ORRs (To be assessed after completing 4 cycles of treatment) in these 11 patients, the study will be stopped for futility. Otherwise, if >=2/11 responses are observed, then 8 additional patients will be accrued for a total of 19. The null hypothesis will be rejected if 4 or more ORRs are observed in

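### Dosed patients who fail in cycle 1 leave the primary ORR and are replaced, which biases it upward; whether cycle-2 stoppers count is unclear

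*Combined protocol and SAP*

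**What the plan says.** Three rules decide who is counted.

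- **Replacement in general** (Sample Size and Statistical Consideration): "Patients who do not complete the planned cycle 2 cycles of treatment, which is required for the first evaluation of response, will be replaced". I read this as two cycles. Just above it, Duration of Treatment shows that stopping is not only a matter of preference: "Patients will be treated until one of the following events: disease progression, unacceptable adverse event(s), withdrawal of consent".
- **Replacement of diet stoppers** (Treatment Plan, Ketogenic diet). The rule for a patient who wants to give up the diet earlier than the point it names reads: "cycle 2 is completed, when the response will be first evaluated, the patient will not be allowed to continue this trial but will be replaced".
- **Evaluability** (Data analysis): "All patients receiving at least one dose of copanlisib will be evaluable for toxicity", whereas "all patients completing at least one 28-day cycle of therapy (copanlisib plus ketogenic diet) will be evaluable for response and time-to-endpoint analyses".

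The Simon rules use fixed numbers. FL continues with 6 or more responses in 13 and succeeds with 14 or more in 23. EC continues with 2 or more in 11 and succeeds with 4 or more in 19. The text does not say whether these are enrolled, dosed, one-cycle or two-cycle patients. Nothing in the public text scores an early failure as a non-responder. Section 5.6 (Withdrawal criteria) is cited but is not in the public text, and it may bear on this.

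**The concern.** Set side by side, the rules treat two groups of dosed patients as follows.

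- **Stopped during cycle 1.** Not evaluable for response, and replaced. The two sections agree. The difficulty is the effect of the rule: a patient whose treatment failed early counts for toxicity, disappears from the efficacy denominator, and is succeeded by someone with a fresh chance of response.
- **Completed cycle 1, stopped in cycle 2.** Evaluable under Data analysis, replaced under the other two rules. Here the text conflicts, because it does not say whether this patient, the replacement, or both belong to the 23 or the 19.

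The count at stake is the primary endpoint in both arms and the stage-1 continuation decision. With 13 and 11 patients, reclassifying one patient can reverse that decision, and an open membership rule could be settled after responses are known. Early failures are foreseeable: the Safety Trigger counts first-cycle deaths and serious first-cycle delays.

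**Working it through.** **Inputs from the protocol.** FL: stop at 5 or fewer of 13, succeed at 14 or more of 23, null 41%, target 67%, stated type I error 5% and power 80%. EC: stop at 1 or fewer of 11, succeed at 4 or more of 19, null 10%, target 30%, stated 10% and 81%.

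**Step 1: reproduce the design.** The probability of success at true rate p is the sum, over stage-1 counts x above the futility bound, of Bin(x; n1, p) × P(Bin(n − n1, p) ≥ r − x), where r is 14 or 4. This gives:

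- FL: type I error 0.0429, power 0.8006.
- EC: type I error 0.0988, power 0.8212.

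The type I errors lie within the stated levels, and the powers agree with the stated figures to about one percentage point. The Simon cut-offs are sound.

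**Step 2: remove and replace early stoppers.** The documents give none of the following, so these are assumptions: 41% and 10% are rates in all treated patients; a share d of dosed patients is removed and replaced; those patients would respond at f times the null rate p0. The rate among the patients counted is then

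pc = p0 × (1 − f·d) / (1 − d).

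For FL with f = 0 and d = 5%, pc = 0.41 / 0.95 = 0.4316. For EC, pc = 0.10 / 0.95 = 0.1053. Putting pc into the Step 1 formula gives these type I errors:

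| f | d | FL (stated 5%) | EC (stated 10%) |
|---|---|---|---|
| any | 0 | 4.3% | 9.9% |
| 0 | 5% | 6.6% | 11.4% |
| 0 | 10% | 10.2% | 13.2% |
| 0.5 | 5% | 5.4% | 10.6% |
| 0.5 | 10% | 6.8% | 11.5% |
| 1 | 5% or 10% | 4.3% | 9.9% |

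The expected number replaced is n·d/(1 − d). At d = 5% that is 23 × 0.05/0.95 = 1.2 in FL and 19 × 0.05/0.95 = 1.0 in EC. At d = 10% it is 2.6 and 2.1. With f = 0 and d = 10%, the chance of a futility stop under the null falls from 54.5% to 41.1% in FL and from 69.7% to 65.0% in EC.

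**Step 3: effect on the estimate.** Suppose FL ends with 14 responses in 23 counted patients: 60.9%, exact 95% interval 38.5% to 80.3%. If two dosed non-responders had been replaced along the way, the rate in all dosed patients is 14/25 = 56.0%, interval 34.9% to 75.6%.

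**Step 4: price of counting all dosed patients.** If 67% and 30% are completer rates and early stoppers never respond, the all-dosed target is p1(1 − d).

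- d = 5%: FL 0.6365, power 0.6910; EC 0.285, power 0.7853.
- d = 10%: FL 0.603, power 0.5648; EC 0.27, power 0.7445.

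If the nulls are completer rates as well, the all-dosed test is conservative: type I error 0.0272 and 0.0165 in FL, 0.0854 and 0.0729 in EC, at d = 5% and 10%.

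**The case against.** The strongest defence is that this is a single-arm pilot and the replacement sentence sits just above the Simon rules. On a plain reading, the 23 and 19 are two-cycle completers and the nulls apply to completers. Error rates then hold, and preferring all dosed patients is a choice of estimand. This stands in part: under completer nulls there is no inflation. But no section says the nulls are completer rates, the evaluability rule uses one cycle and not two, and the ORR would describe a selected group.

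It is also fair that d and f are assumptions, that Section 5.6 could settle membership, and that replacing diet stoppers was deliberate.

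Three stronger readings are tempting and are not supported.

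- A reader might infer that the sections contradict each other on cycle-1 failures. They agree; the rule is biased, not inconsistent.
- A reader might infer that the Simon denominators are undefined. The numbers are fixed; only membership is open.
- A reader might infer that counting both a cycle-2 stopper and the replacement, with cut-offs unchanged, inflates error even when stoppers are not poor responders. That needs a documented response before cycle 2 ends. The protocol places the first evaluation at the end of cycle 2, and under Efficacy Outcome "CT or PET/CT scan will be performed after every two 28-day cycles"; no earlier assessment is scheduled. A stopper with no documented response adds nothing to the response count, so this reading merely repeats the f = 0 removal case.

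**Conclusion.** The concern holds in a limited form. As written, the plan takes dosed cycle-1 failures out of the primary ORR and replaces them, and it leaves open whether cycle-2 stoppers are among the 13/23 and 11/19. The selection follows from the text and needs no assumption about rates.

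The size of the type I error inflation is conditional on all-treated nulls and on replaced patients responding less often than the null rate. At assumed replacement shares of 5% to 10%, type I error is 5.4% to 10.2% in FL against a stated 5%, and 10.6% to 13.2% in EC against a stated 10%. The lower ends are for half-rate responders and the upper ends for patients who never respond. FL is the more sensitive arm. The design calculations themselves are correct.

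**What to change.** In Sample Size and Statistical Consideration and in Data analysis, define one primary ORR population per arm: all patients who receive at least one dose of copanlisib. Then:

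- State that 13, 23, 11 and 19 refer to that population.
- Count any dosed patient without a documented CR or PR as a non-responder, including those who stop early for progression, death or toxicity, and do not replace them in the Simon counts.
- Limit replacement in those counts to patients never dosed, such as run-in failures.
- State how dosed patients who leave only because of the diet are counted. Non-responder in the primary analysis is consistent with the rest, and should be acknowledged as an estimand choice.
- Report completer ORR as a labelled sensitivity analysis.
- State whether 41%/67% and 10%/30% are all-treated or completer rates.
- Reconcile the Ketogenic diet, Sample Size and Data analysis text, and Section 5.6, with this definition.

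As a secondary matter, the one-cycle filter also covers the time-to-event analyses, so the PFS population should be aligned. PFS and OS are not listed objectives, and for OS the plan says only "Overall survival will be assessed post hoc in the trial patients".

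The change adds no procedures and does not alter who stays on treatment. It does have a cost: the reported ORR will be lower than the completer ORR. If the target rates are completer rates and early stoppers never respond, power is about 69% (FL) and 79% (EC) at d = 5%, and 56% and 74% at d = 10%. The protocol should state this loss or re-derive the sample size.

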As we recently reported ketogenic diet can suppress hyperinsulinemia associated with PI3K inhibitors, leading to potentiation of the anti-tumor effects of PI3K inhibitors[79]. Copanlisib potently inhibits PI3K α and PI3K δ . It has been approved for the treatment of relapsed follicular lymphoma, based on ORR of 59% (84 of 142 patients)[83]. The CR rate in FL was 14%, and the median progression-free survival was 11.2 months. Copanlisib demonstrated encouraging clinical activity in marginal zone lymphoma (ORR 70% including 9% CR). While these results are clinically meaningful, FL and MZL inevitably develop resistance to copanlisib with time, even in those patients who initially respond to the therapy. Novel strategies to improve the efficacy of copanlisib in FL and MZL, by improving CR and PFS, may transform how we manage these incurable malignancies.

Interestingly, copanlisib has also demonstrated clinical activity in aggressive lymphomas in a smaller study of heavily pre-treated patients[84]. Objective responses were achieved in patients with DLBCL (one PR; ORR 6.7%), PTCL (two CRs, one PR; ORR 21.4%), MCL (two uCRs, five PRs; ORR 63.6%), and transformed FL (both PRs; ORR 33.3%). These results suggest that copanlisib warrants further investigation in aggressive lymphomas such as PTCL and DLBCL. In a Phase I study of both solid tumors and lymphoma, sixteen of 20 patients treated at the MTD had reduced ⁽¹⁸⁾FDG-PET uptake; 7 (33%) had a reduction >25%. One patient achieved a complete response (CR; endometrial carcinoma exhibiting both PIK3CA and PTEN mutations and complete PTEN loss) and two had a partial response (PR; both metastatic breast cancer). Among the nine NHL patients, all six with follicular lymphoma (FL) responded (one CR and five PRs) and one patient with diffuse large B-cell lymphoma had a PR by investigator assessment; two patients with FL who achieved CR (per post hoc independent radiologic review) were on treatment >3 years.

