The exact mechanism of resistance to copanlisib in various lymphomas and solid tumors remain poorly understood. As described above, we have reported that PI3K inhibitors can induce hyperinsulinemia, which in turn leads to activated survival pathway in cancer cells[79]. Our preliminary results demonstrate that in mice copanlisib stimulated the blood level of insulin, which is effectively mitigated by the ketogenic diet. Importantly, the ketogenic diet markedly improves the survival of KPC mice treated with copanlisib (BAY 80-6946).

Collectively, the results presented above suggest that copanlisib may have encouraging clinical activity in indolent B-cell NHL such as FL and MZL, aggressive lymphomas such as PTCL and DLBCL, and solid tumors such as endometrial cancer. Furthermore, ketogenic diet may mitigate hyperinsulinemia associated with copanlisib in many patients, leading to improved treatment response to copanlisib and prolonged patient survival.

Fasting requirements and pre-dose glucose levels

Period	Fasting ≥ 8 hrequiredbeforefirstglucosemeasurement	Pre-dose glucose levels (first glucose measurement)
Day 1 Cycle 1	Yes	≤ 125 mg/dL (non-diabetic patients)
		<160 mg/dL (diabetic patients)
Subsequent Infusion after Day 1 Cycle 1	No ^a	<160 mg/dL (fasting) < 200 mg/dL (non-fasting)

^aThe decision regarding meal timing and fasting can be made by the investigator based on glucose response patterns during prior treatment days

The investigator will accurately document fasting/non-fasting for each glucose measurement done at the site.

• Fasting refers to no caloric intake for ≥ 8 h.

• Non-fasting status includes any caloric intake such as meals and also juice, snacks, and other caloric intake not consistently called a meal.

From Cycle 1 Day 1 onwards, glucose measurements at the site may be done either by laboratory analysis or in capillary blood using a hand-held glucose meter. If hand-held capillary glucose meters are chosen, the appropriate calibration of glucose meters will be documented. Any capillary or plasma glucose of > 250 mg/dL should be confirmed by repeated laboratory analysis.

Laboratory criteria for dosing of copanlisib

Blood glucose must be performed and assessed on the day of infusion. Glucose lowering medication can be used to optimize pre-infusion glucoses.

Laboratory tests must be performed and assessed prior to each infusion of copanlisib. The results can be done +/- 2 days.

Laboratory Test	Criteria

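### Does a 41% null near the bottom of the protocol's own 40–59% copanlisib range make a positive FL result unsound?

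*Combined protocol and SAP*

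**What the plan says.** Under Sample Size and Statistical Consideration, item (a), the synopsis states: "The null hypothesis that the true ORR rate is 41% will be tested against a one-sided alternative". Stage one takes 13 patients; with 5 or fewer responders the arm stops, otherwise 10 more patients are added, and 14 or more responders of 23 reject the null. The stated type I error is 5% and the power 80% at a true ORR of 67%.

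The next bullet gives the context: "The reference range of ORR in FL is 40% (n = 16", with an upper end of 59% attributed to 104 patients. The Study Rationale describes copanlisib's approval as "based on ORR of 59% (84 of 142 patients").

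The primary objective for this arm is to determine ORR. The rationale hopes that the diet will reduce hyperinsulinaemia, "leading to improved treatment response to copanlisib and prolonged patient survival". Under Data analysis: "Response will be estimated with exact 95% confidence intervals (CIs"). There is no copanlisib-alone arm.

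**The concern.** The diet is the new element, and the reference rates are the only yardstick for copanlisib without it. A null one point above the lower reference rate and 18 points below the upper one keeps the error at 5% only if copanlisib alone has an ORR of about 41.7% or less. If the larger study's 59% is nearer the truth, a diet with no effect would still give a positive arm about half the time.

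The planned interval does not obviously settle the matter, because no bound or comparison rate is named. The one-sided 5% test and a two-sided 95% interval can also disagree: at 14 of 23 the test rejects 41%, while the two-sided lower limit is 38.5%. At stake is whether a positive result could be reported as evidence for the diet when it shows only that the combination exceeds 41%.

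**Working it through.** **Inputs** (Sample Size and Statistical Consideration, item (a)): first stage 13, continue with 6 or more responders; second stage 10; reject at 14 or more of 23; null 41%; alternative 67%; reference range 40% to 59%.

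**Formula.** For a true ORR *p*:

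P(reject | *p*) = Σ (x = 6 to 13) Bin(x; 13, *p*) × P(Y ≥ 14 − x), with Y ~ Bin(10, *p*).

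**Plan's own figures.** At *p* = 0.41 the terms for x = 6 to 13 are 0.0030 + 0.0088 + 0.0135 + 0.0111 + 0.0051 + 0.0013 + 0.0002 + 0.0000 = 0.0429 (summed before rounding). At *p* = 0.67 the sum is 0.8006. Both agree with the stated 5% ceiling and 80%. A cut of 13 would give 9.4% at 41%, so 14 is the right boundary.

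**The same rule at other true ORRs:**

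| True ORR | P(reject) |
|---|---|
| 40% | 3.5% |
| 41% | 4.3% |
| 41.74% | 5.0% |
| 45% | 9.3% |
| 50% | 20.1% |
| 55% | 36.1% |
| 59% | 51.4% |
| 67% | 80.1% |

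The two accounts of the 59% (104 patients, or 84 of 142) make no practical difference: 61/104 = 58.7% (the nearest count, an assumption) gives 50.0%, and 84/142 = 59.2% gives 52.0%. The lower end is softer, because no count of 16 equals 40%: 6/16 = 37.5% gives 1.9% and 7/16 = 43.75% gives 7.4%.

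**What a positive result would exclude.** Exact (Clopper–Pearson) lower limits with 23 patients:

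| Responders | One-sided 95% | Two-sided 95% |
|---|---|---|
| 14 | 41.7% | 38.5% |
| 15 | 46.0% | 42.7% |
| 16 | 50.4% | 47.1% |
| 17 | 54.9% | 51.6% |
| 18 | 59.6% | 56.3% |
| 19 | 64.5% | 61.2% |

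Results of 14 to 17 reject 41% without excluding 59%. Their probability is 0.8006 − 0.1781 = 0.62 at a true ORR of 67%, and 0.5138 − 0.0443 = 0.47 at 59%.

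**What a bar at 59% would do.** Requiring 18 of 23 gives an error of 4.4% at 59% and power of 17.8% at 67%. Requiring 19 gives 1.5% and 8.1%. The counts also depend on the denominator. Data analysis makes patients evaluable for response after one cycle, while the sample-size text says: "Patients who do not complete the planned cycle 2 cycles of treatment, which is required for the first evaluation of response, will be replaced". A replaced patient could therefore still be evaluable. With 24 or 25 evaluable patients, 18 responders give one-sided lower limits of 56.5% or 53.8%, both below 59%.

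**The case for a change.** The strongest case for a change is that the likely positive result is the ambiguous one. At the design alternative, 62% of trials end with 14 to 17 responders, a result that cannot separate a working diet from copanlisib alone at 59%. The rationale speaks of better response to copanlisib, the text gives no reason for choosing 41%, and a sentence limiting the conclusion would cost nothing. Choosing a confidence bound after seeing the data would leave room for either reading at 18 of 23.

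The arithmetic stands, and so does the point that 23 uncontrolled patients say little about the diet's own contribution. What does not follow is that the plan must change. Any single-arm test limits error only at or below its null, and a reader who sees the null beside a 40–59% range can see that limit. A sentence saying so would be harmless, but it would alter no decision, boundary or estimate.

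A 59% bar is the only suggestion that adds a rule, and it is a poor bargain. It treats an estimate as fixed, although the exact 95% interval for 61/104 is about 49% to 68%. It also implies that a diet effect could be claimed above the bar. That comparison would be uncontrolled, and entry to treatment is selective: "Only patients who demonstrate compliance and tolerance with the ketogenic diet for all 7 days during the run-in" phase go on to copanlisib, and early non-completers are replaced.

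**Conclusion.** No change is needed. The error and power are correct at the stated null and alternative, and the conclusion that the test licenses, ORR above 41%, matches an objective of determining ORR in a pilot study. How far such a result speaks to the diet is a matter of interpretation. Analysts can handle it by reporting the exact interval against the printed reference range. The differing denominators for the 59% are a citation matter that moves the rejection probability only between 50.0% and 52.0%.

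The 3.5% to 51.4% range assumes that the reference rates apply to this population and to the same assessment time. The plan specifies response after four cycles at stage one; the documents do not say when the reference responses were assessed. The diet run-in and the replacement of early non-completers are not modelled. That no text limits what rejection may conclude can be confirmed only for the supplied synopsis and rationale, which point to protocol sections that are not included.
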